13.2. Appendix 2: Assessment Windows

13.2.1. Definitions of Assessment Windows for Analyses

No Assessment Windows will be defined for Analysis, and summaries and analyses will be based on nominal visits.

207546

13.3. Appendix 3: Study Phases and Treatment Emergent Adverse Events

13.3.1. Study Phases for Parts A and C

Assessments and events will be assigned to the relevant treatment Period dependent on whether they are spontaneous events (i.e. data collected in a log such as Adverse Events and Concomitant Medications, and Disposition) or planned events (i.e. data with timeslicing assigned such as ECG, Laboratory, and Vital Signs).

Spontaneous events are assigned to period according to the time of occurrence relative to the start date/time of the study treatment within the period up to, but not including, the start date/time of the study treatment in the next period. Planned assessments, including unscheduled visits are assigned to period according to the date of first visit of that period (including Day -1 and Day -10 assessments as applicable) up to the day prior to the first visit of the next period or day prior to Follow-Up visit (including Day -1 and Day -10 assessments as applicable).

For planned events, assessments prior to the date of first visit in Period 1 for Part A (or Period 7 for Part C) are assigned as Screening. For spontaneous events, events prior to the datetime of first dose in Period 1 for Part A are assigned as Pre-Treatment (or Period 7 for Part C).

For planned events, assessments on or later than date of first Follow-Up visit are assigned as Follow-Up. For spontaneous events, events later than date of last dose + 7 days are assigned as Follow-Up.

Study Phase	Definition
Prior	If medication end date is not missing and is before 28 days prior to
	screening visit
Concomitant	Any medication that is not a prior
1. NOTE:	

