Further details of the DEC remit are provided in Section 12.3 and in the Dose Escalation Plan (DEP). This plan outlines how the study team will ensure data integrity used in dose selection decisions by performing clinical data review and appropriate quality control of data prior to making dose selection decisions, as well as outlining the responsibilities of the investigators and site staff for reporting safety data, participation during dose escalation meetings, and confirmation that the data used for dose escalation are accurate and complete.

Further information on dose decisions / modifications is provided in Section 7.2.

5.1.1.2. Part A LPS or GM-CSF challenge with cantharidin-induced blisters – Cohort 1 and Cohort 2:

Upon conclusion of the dose escalation phase of Part A, an additional dosing Period (treatment Period 4) will be included. Eligible participants in both cohorts will attend the clinic for outpatient visits, on Day -10 (\pm 3 days) to have control blisters induced on the

forearm (0.2% cantharidin), and will have a blister sample taken at approximately 48hrs post-blister induction. Participants in Cohort 1 will be administered an IV *in vivo* LPS challenge at a dose of 0.75 ng/kg following treatment with GSK3358699 or placebo and will then have blisters induced on the forearm (0.2% cantharidin) approximately 20 minutes after the challenge. Similarly, participants in Cohort 2 will be administered 60 μ g/m² *in vivo* GM-CSF challenge as an IV infusion following treatment with GSK3358699 or placebo and will then have blisters induced on the forearm (0.2% cantharidin) approximately 20 minutes after the challenge. Similarly, participants in Cohort 2 will be administered 60 μ g/m² *in vivo* GM-CSF challenge as an IV infusion following treatment with GSK3358699 or placebo and will then have blisters induced on the forearm (using 0.2% cantharidin) approximately 20 minutes after the end of the GM-CSF infusion. Of the nine participants within each cohort, six will receive GSK3358699 and three will receive placebo in treatment Period 4, as per the randomisation schedule.

The duration of treatment Period 4 from Day -1 onwards and the implementation of sentinel dosing will be the same as for each of treatment Periods 1-3. The dose levels of GSK3358699 administered to either cohort in treatment Period 4 will be identical and will be decided by the DEC.

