The doses of LPS and GM-CSF to be administered to participants have been defined as part of a clinical enabling study [GlaxoSmithKline Document Number 2016N309726_01 Study ID 207654] and will be administered at the GSK3358699 systemic C_{max} defined from data gathered in treatment Periods 1-3. The dose levels of GSK3358699 administered to either cohort in treatment Period 4 will be identical. This will be a single dose of GSK3358699 that is within the range investigated in treatment Periods 1-3 of Part A and the decision on the dose level will be made by the DEC based on all available safety, tolerability, PK and PD data from treatment Periods 1-3.

The *in vivo* challenges included in treatment Period 4 will act as a pre-determinant to their inclusion in Part C. That is, if GSK3358699 treatment does not robustly inhibit production of inflammatory mediators and leukocyte activation following either low dose *in vivo* LPS or GM-CSF challenges and blisters in Part A, the same challenge will not be investigated in Part C. Inclusion of challenges in Part C will be decided once all the data has been generated from treatment Period 4 in Part A, and the criteria will be specific for each challenge. Inclusion of the challenges in Part C will be based on inhibition of multiple inflammatory biomarkers which may include, but are not limited to, TNF, IL-6, MCP-1 and CRP for the LPS challenge, leukocyte activation markers, thymus and activation regulated chemokine (TARC) and Macrophage-Derived Chemokine (MDC) for the GM-CSF challenge, and leukocyte counts, interferon gamma-induced protein-10 (IP-10), MMP-9, transforming growth factor (TGF)- β and leukocyte activation markers for the cantharidin-induced blisters.

5.1.1.3. Part A Dose Escalation / Challenge Total Duration:

There will be a minimum of 14 days between each dosing in Cohort 1 and Cohort 2 to ensure that appropriate dose decisions can be made during the dose escalation phase. This results in a minimum 28 day washout Period between dosing in each treatment Period for a particular cohort (including between treatment Periods 3 and 4).

The total duration of this part of the study for each participant, including screening and follow-up, is approximately 19 weeks for participants taking part in all three dose escalation treatment Periods and 23 weeks if a participant takes part in all four treatment

[figure not shown]

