 will be recruited for treatment Period 4 only and will be regarded as a replacement participant. If a subject prematurely discontinues the study during Part A, additional replacement participants will be recruited and assigned to the same treatment sequence, starting from the next planned dosing Period following the premature discontinuation. Staggering of the first two participants (sentinel dosing) will be implemented in each cohort in each treatment period for this single dose phase. No participant will be a sentinel participant more than once. On Day 1, one of the two participants will receive the active dose and the other will receive placebo. Assuming adequate safety from these two participants over the first 48 hrs post-dose, the remaining participants in the cohort can then be dosed. Data, and hence dose level, will be reviewed between each period. There will be a minimum 14 days between the start of dosing (i.e. dosing of sentinel participants) in Cohort 1 and Cohort 2 in each treatment period. The decision to proceed to the next dose level of GSK3358699 will be made at a Dose Escalation Committee (DEC) meeting Upon conclusion of the dose escalation phase of Part A, an additional dosing period (treatment period 4) will be included. Participants in both cohorts will attend the clinic for outpatient visits, on Day -10 (± 3 days) to have control blister sample taken at a timepoint between approximately 48hrs post-blister induction. Participants in Cohort 1 will be administered an IV in vivo LPS challenge at a dose of 0.75 ng/kg following treatment with GSK3358699 or placebo and will then have blisters induced on the forearm (0.2% cantharidin) approximately 20 minutes after the challenge. The final selection of LPS dose will take into account all available pre-clinical and clinical safety and PD data at the time of study initiation. Participants in Cohort 2 will be administered 60 µg/m² in vivo GM-CSF challenge as an IV infusion followin
Refer to Appendix 1: Schedule of Activities

[figure not shown]
Part A: Sing	le Ascendi	ng Dose	es and L	PS / GN	-CSF challe	nges		
Part A	• Illust	ration o	f actual	treatme	nts after do	se escalation	on in Part	A.
Treatmen			Perio		Period		Period	1
t	Cohort	N=3	Р		10mg		40mg	
sequences	1	N=3	1mg		P		40mg	
-		N=3	1mg		10mg		P	
	Cohort	N=3	Ŭ	Р		20mg		30mg
	2	N=3		3mg	ξ	Р		30mg
		N=3		3mg	5	20mg		Р

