8.1. Adverse Events Analyses

The definition of an AE is detailed in Appendix 4 of the protocol.

Analyses of AEs will include all events, classified as in Section 13.3.

Adverse events analyses including the analysis of adverse events (AEs), Serious (SAEs) and other significant AEs will be based on GSK Core Data Standards.

Details of the planned displays are presented in Appendix 9: List of Data Displays.

207546

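### SAP 13.3.1 gives Part A adverse events unequal attribution windows and places events after the Period 4 control blisters under the Period 3 treatment

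*SAP*

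**What the plan says.** SAP 13.3.1 has one rule for spontaneous events, which include adverse events, and another for planned assessments.

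- **Adverse events, general rule.** They belong to a period from its dose "up to, but not including, the start date/time of the study treatment in the next period".
- **Adverse events after the last dose.** "For spontaneous events, events later than date of last dose + 7 days are assigned as Follow-Up".
- **Planned assessments.** They are placed "according to the date of first visit of that period (including Day -1 and Day -10 assessments as applicable"), so a Day -10 assessment counts in Period 4.

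Protocol 5.1.1.3 sets the spacing: "This results in a minimum 28 day washout Period between dosing in each treatment Period for a particular cohort", and it includes the gap between Periods 3 and 4. For the control blisters before Period 4, Protocol 5.1.1.2 states: "Eligible participants in both cohorts will attend the clinic for outpatient visits, on Day -10", with an allowance of 3 days either way.

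On which events are analysed, SAP 8.1 states: "Analyses of AEs will include all events, classified as in Section 13.3". SAP 13.3.2 defines a treatment-emergent flag that runs from treatment start to one day after treatment stop. No Part A adverse-event table in SAP 13.9.5, nor Figure 2.1 in 13.9.6, says that it is restricted to flagged events.

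**The concern.** Safety and tolerability are the primary objective, and Part A is read by comparing treatment columns. If the time during which an event can be credited to a treatment differs between columns, or between participants within one column, event counts differ for reasons unrelated to drug.

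Two features stand out. First, a day-10 event after 40 or 30 mg is credited to that dose only if the participant later enters Period 4, which is optional; attribution then depends on something that happens after the event. Second, one procedure visit is split: measurements at the control-blister visit belong to Period 4, while an adverse event caused by the blister belongs to the Period 3 treatment. With six active participants planned per dose level in Periods 1 to 3, one misplaced participant moves a column by 1/6, about 17 percentage points.

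**Working it through.** **Inputs.** Gap between the two interlocking cohorts (Protocol 5.1.1.3): "There will be a minimum of 14 days between each dosing in Cohort 1 and Cohort 2". Cut-off after the last dose: 7 days (SAP 13.3.1). Control-blister visit: Day -10 with 3 days' allowance (Protocol 5.1.1.2; SAP 2.3). Doses actually used: 1, 3, 10 and 20 mg in Periods 1 and 2; 40 mg (Cohort 1) and 30 mg (Cohort 2) in Period 3; 25 mg in Period 4 (SAP 2.3 and 5.2). Event collection: first dose to final follow-up (Protocol schedules of activities and 9.2.1).

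**Step 1: reproduce the 28 days.** Two cohorts alternate, so the interval within a cohort is 2 x 14 = 28 days, as stated. The synopsis counts it between sentinel doses, so an individual's gap can differ by a day or two.

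**Step 2: windows by treatment under SAP 13.3.1.**

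| Treatment | Window |
|---|---|
| 1, 3, 10, 20 mg | at least 28 days; 7 if the participant withdraws before another dose |
| 40 mg, 30 mg | at least 28 days if he enters Period 4; 7 if he stops |
| 25 mg | 7 days |
| Placebo | a mixture of both, by period |

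Ratio of windows: at least 28/7 = 4.

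**Step 3: does it depend on where Follow-Up events are displayed?** The SAP does not say. If they are shown apart from the doses, Step 2 stands. If they are shown under the last treatment, 25 mg is followed to the second follow-up visit, about 5 x 7 = 35 days, and its short window disappears. A participant who stops after Period 3 has only the first follow-up visit, at 7 to 14 days, because the second is for challenge participants. His window would be 7 to 14 days against at least 28 for one who continues, so the discrepancy within 30/40 mg remains either way.

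**Step 4: control blisters.** The visit falls 10 - 3 = 7 to 10 + 3 = 13 days before the Period 4 dose. With the minimum interval, that is 28 - 13 = 15 to 28 - 7 = 21 days after the Period 3 dose. The stretch from blister to Period 4 dose is 7/28 = 25% to 13/28 = 46% of the Period 3 window. An event starting in it precedes the Period 4 dose, so the general rule puts it under 40 mg, 30 mg or placebo. A longer interval moves the visit further from the Period 3 dose but not out of its window.

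**Step 5: illustration only.** The documents give no background event rate. Assume a constant rate r per person-day and no drug effect; then P(at least one event) = 1 - exp(-r x days).

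| r | 28 days | 7 days |
|---|---|---|
| 0.002 | 5.4% | 1.4% |
| 0.005 | 13.1% | 3.4% |
| 0.01 | 24.4% | 6.8% |
| 0.02 | 42.9% | 13.1% |

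**Step 6: after the fix.** With 7 days for every period the ratio is 7/7 = 1, and the blister visit, at day 15 or later, lies outside every Period 3 window.

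**The case against.** The strongest reply is that an equal-window rule already exists. The treatment-emergent flag covers the dose day and the day after in every single-dose period, and would keep control-blister events out of Period 3. SAP 8.1 refers to Section 13.3, which contains the flag, and the display shells are in separate documents. That leaves open which displays use it. It does not settle the matter: 8.1 says that all events are analysed, and no listed Part A adverse-event table or Figure 2.1 mentions the flag.

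One could also read cantharidin as study treatment, since Protocol Table 5 lists it under that label; Period 4 would then begin at the blister visit. SAP 13.3.1 names Day -10 only for planned assessments, and the treatments in SAP 5.2 are GSK3358699 and placebo.

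Several limits on the point do stand:

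- The 7-day window for 25 mg depends on an unstated display rule (Step 3).
- The drug-related tables (2.2, 2.7, 2.8) are partly protected, because the investigator weighs timing and other causes.
- The blister point concerns only participants dosed in both Periods 3 and 4. For Period 4-only replacements the blisters precede the first dose, before adverse-event collection begins.
- The summaries are descriptive, and Listing 12 shows every event.

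A reader might infer that background events pile up under low doses and so hide a rise with dose. The documents do not support that. The 1 to 20 mg doses share one rule, 25 mg is not the top dose and is given with a challenge anyway, and blister events would push 30/40 mg in the opposite direction.

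**Conclusion.** The point holds as a defect of attribution. Under SAP 13.3.1 as written, windows differ between 1-20 mg and 25 mg (subject to the display of Follow-Up events), within 30/40 mg according to later participation, and within placebo. Control-blister events in participants dosed in both Periods 3 and 4 are credited to the Period 3 treatment, against the SAP's own handling of planned assessments at that visit.

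The only size that follows from the documents is the ratio of windows, at least 4:1 at the protocol's minimum spacing. It is not a fourfold difference in event rates. The probabilities in Step 5 rest on an assumed, constant rate; constancy is doubtful, because in Periods 1 to 3 no visit is scheduled between Day 3 and the next period's admission, so ascertainment in washout is likely to be weaker than in the unit. The direction and size of the effect on the dose comparison are not known. The displays most exposed are the by-treatment all-event tables and the relative-risk plot, Figure 2.1.

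**What to change.** Amend SAP 13.3.1 in two places.

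1. Assign adverse events that start from control-blister induction up to Period 4 dosing to a separate control-blister phase, not to the Period 3 treatment.
2. Use one common post-dose window for every Part A dose and placebo period in the by-treatment all-event tables and Figure 2.1. It can be the 7 days already used after the last dose, or the treatment-emergent flag of 13.3.2. Show later events, from every period, in a separate washout/follow-up column, and keep all events in the listings. This also settles where Follow-Up events appear.

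The cost is SAP wording and one re-derived period variable; no new data are needed. The downside is small: late-onset events leave the dose columns, which matters in a first-in-human study, but they remain visible in the washout/follow-up column and in the listings.

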13.3.1.1. Study Phases for Concomitant Medication

- Refer to Appendix 6: Reporting Standards for Missing Data for handling of missing and partial dates for concomitant medication. Use the rules in the table above if concomitant medication date is completely missing.
- Pre-trial medications are assumed concomitant if the stop date is within 28 days of the screening visit.

207546

13.3.2.	Trea	tment Emergent Flag for Adverse Events
Flag		Definition

Flag	Definition
Treatment Emergent	• If AE onset date is on or after treatment start date & on or before treatment stop date +1.
	 For crossover parts (Part A), if AE onset is during one period and worsens during a later period it would be counted in both periods. For the initial period the logic would be as above. For the later period the logic would use the treatment dates associated with the later period:
	Treatment Period Start Date \leq AE Worsening Date \leq Study Treatment Stop Date + 1 days.

NOTES:

- If the AE start/worsening date is on or after treatment start date, and treatment stop date is missing, then the AE will be considered to be Treatment Emergent.
- Time of study treatment dosing and start/stop time of AEs should be considered, if • collected.

207546

13.4. Appendix 4: Data Display Standards & Handling **Conventions**

13.4.1. **Reporting Process**

Software

Software				
• The currently supported versions of SAS software will be used.				
Reporting Area				
HARP Server	: UK1SALX00175			
HARP	: \arprod\gsk3358699\mid207546\data_look_01			
Compound	: \arprod\gsk3358699\mid207546\final_01			
Analysis Datasets				
• Analysis datasets will be created according to Integrated Data Standards Library				

Analysis datasets will be created according to Integrated Data Standards Library (IDSL) Legacy GSK A&R dataset standards.

Generation of RTF Files

RTF files will be generated for all tables within the final 01 reporting effort for SAC. •

13.4.2. **Reporting Standards**

General

The current GSK Integrated Data Standards Library (IDSL) will be applied for • reporting, unless otherwise stated (https://spope.gsk.com/sites/IDSLLibrary/SitePages/Home.aspx): 4.03 to 4.23: General Principles 5.01 to 5.08: Principles Related to Data Listings • 6.01 to 6.11: Principles Related to Summary Tables • 7.01 to 7.13: Principles Related to Graphics • Do not include participant level listings in the main body of the GSK Clinical Study Report. All participant level listings should be located in the modular appendices as ICH or non-ICH listings All data displays (Tables, Figures and Listings) will use the term "Subject" which • reflects CDISC and GSK data display standards terminology. Formats • GSK IDSL Statistical Principles (5.03 & 6.06.3) for decimal places (DPs) will be adopted for reporting of data based on the raw data collected, unless otherwise stated. Numeric data will be reported at the precision collected on the eCRF. • • The reported precision from non eCRF sources will follow the IDSL statistical

principles but may be adjusted to a clinically interpretable number of DP's. Planned and Actual Time

- Reporting for tables, figures and formal statistical analyses: •
 - Planned time relative to dosing will be used in figures, summaries, statistical • analyses and calculation of any derived parameters, unless otherwise stated.

207546

- The impact of any major deviation from the planned assessment times and/or scheduled visit days on the analyses and interpretation of the results will be assessed as appropriate.
- Reporting for Data Listings:
 - Planned and actual time relative to study drug dosing will be shown in listings (Refer to IDSL Statistical Principle 5.05.1).
 - Unscheduled or unplanned readings will be presented within the participant's listings.

Unscheduled Visits

- Unscheduled visits will not be included in summary tables and figures.
- All unscheduled visits will be included in listings.

Descriptive Summary Statistics

Continuous Data Refer to IDSL Statistical Principle 6.06.1 – do not report 95% CI unless otherwise specified.

Categorical Data N, n, frequency, %

Graphical Displays

• Refer to IDSL Statistical Principals 7.01 to 7.13.

207546

Pharmacokinetic	Concentration Data
PC Windows	PC WNL file (CSV format) for the non compartmental analysis by
Non-Linear	Clinical Pharmacology Modelling and Simulation function will be
(WNL) File	created according to PKOne standards.
	Note: Concentration values will be imputed as per GUI_51487
Descriptive	Refer to IDSL PK Display Standards.
Summary	Refer to IDSL Statistical Principle 6.06.1.
Statistics,	Note: Concentration values will be imputed as per GUI_51487 for
Graphical	descriptive summary statistics/analysis and summarised graphical
Displays and	displays only.
Listings	
Pharmacokinetic	Parameter Derivation
PK Parameter to	N, n, geometric mean, 95% CI of geometric mean, standard deviation
be Derived by	(SD) of logged data and between subject geometric coefficient of
Programmer	variation (CVb (%)) will be reported.
	$\text{CVb}(\%) = \sqrt{(\exp(\text{SD}^2) - 1) * 100}$
	$(SD = SD \text{ of } \log \text{ transformed } \text{ data})$
Pharmacokinetic	Parameter Data
Is NQ impacted	No
PK Parameters	
Rule Being	
Followed	
Descriptive	Refer to IDSL PK Display Standards.
Summary	Refer to Standards for the Transfer and Reporting of PK Data using
Statistics,	HARP.
Graphical	
Displays and	
Listings	

13.4.3. Reporting Standards for Pharmacokinetic

207546

13.5. Appendix 5: Derived and Transformed Data

13.5.1. General (Parts A and C)

Multiple measurements at one analysis time point		
 Mean of the measurements will be calculated and used in any derivation of summary statistics but if listed, all data will be presented, except for blood pressure measurements as only the average of the 3 blood pressure readings will be recorded on the CRF. Subjects who have both high and low values for Normal Ranges at any post-baseline visit for safety parameters will be counted in both the High and Low categories of "Any visit post-baseline" row of related summary tables. This will also be applicable to relevant Potential Clinical Importance summary tables. 		
Study day		
 Calculated as the number of days from first dose date: ref date = missing → study day = missing ref date < first dose date → study day = ref date - first dose date ref date ≥ first dose date → study day = (ref date - first dose date) + 1 		
 Age Birth date will be presented in listings as 'YYYY'. Only the year of birth will be captured, and therefore the date of birth is then derived as follows: Year of birth = YYYY → Date of birth = 30th June YYYY Age calculated based on the data of screening date: Age = integer part (date of screening – 30th June YYYY) / 365.25. Body Mass Index (BMI) 		
Calculated as Weight (kg) / [Height (m) ²]		

